5.6.2 Unscheduled visit

An unscheduled visit (UNS) is a spontaneous visit and may take place at any time during the course of the clinical trial if and when the Investigator deems it necessary. The UNS assessments are detailed in [Table 6-1](#) and must be recorded in the eCRF.

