5.6.2.1 Study Discontinuation visit

Patients who discontinue study participation for reasons cited either by the patient or Investigator should return to the study site for a study discontinuation completion (SDC) Visit. The SDC Visit should be scheduled to occur as soon as possible or at least within 14 Days of the last fingolimod treatment. In case this Visit does not occur within 14 Days then the date when the patient returns must be documented and reported in the SDC eCRF. At the SDC Visit, assessments will be performed as per the assessment schedule as outlined in [Table 6-1](#).

After SDC, at a minimum, in abbreviated visits, the following data should be collected at clinic visits or via telephone visits:

- Adverse events/Serious Adverse Events

If the patient cannot or is unwilling to attend any visit(s), the site staff should maintain regular telephone contact with the patient, or with a person pre-designated by the patient. This telephone contact should preferably be done according to the study visit schedule.

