2.1.1 General definitions

As described in the study protocol, fingolimod treatment refers to Fingolimod 0.5 mg/per day.

The last available assessment on or prior to the reference start date is taken as baseline assessment.

For quantitative measurements,

Change from Baseline will be calculated as:

$$\text{Change from baseline} = \text{Test Value at Visit X} - \text{Baseline Value}$$

The date of first administration of fingolimod treatment (Day 1) is defined as the first date when a non-zero dose of fingolimod treatment was administrated. For the sake of simplification, the date of first administration of fingolimod treatment will be also referred to start date of fingolimod treatment.

The date of last administration of fingolimod treatment is derived as the last date on or prior to cut-off date when a non-zero dose of fingolimod treatment was administrated.

The study day describes the day of the event or assessment date, relative to the reference start date (start date of fingolimod treatment or randomization date depending on the type of assessment). The study day will be displayed in data listings. For summaries of vital signs, physical examinations, laboratory data, ECG, etc., assessments will be assigned to a visit based on windowing. Observations from Day 2 through Day 135 will be assigned to the 3-month visit. Days 136 through Day 270 will be assigned to the 6-month visit, and Days 271 and beyond will be assigned to the 12-month visit. If more than one observation occurs within a given window, the one closest to the target day will be used.

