2.2 Analysis sets

Enrolled Set: All patients enrolled in one of the two cohorts will be included in the Enrolled Set.

Safety Set: The Safety Set will include all patients who enrolled in one of the two cohorts and received at least one dose of fingolimod during the study. Patients will be analyzed according to the cohort enrolled.

Full Analysis Set: For this study, the Full Analysis Set is the same as the safety set defined above.

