2.7 Analysis of the primary objective

2.7.1 Primary endpoint

All analyses will be conducted by cohort for the Safety Set. There are 22 primary endpoints for this study, and Change from Baseline to Month 6 will be calculated as:

Change from baseline to Month 6 = Observed Value at Month 6 (Days 136 to 270) – Baseline Value

1. Change from Baseline to Month 6 in CD4+ naïve T cells (CCR7+CD45RA+)
2. Change from Baseline to Month 6 in CD4+ central memory T cells (CCR7+CD45RACD45RO+)
3. Change from Baseline to Month 6 in CD4+ effector memory T cells (CCR7-CD45RACD45RO+)
4. Change from Baseline to Month 6 in CD4+ Th1 cells (CXCR3+)
5. Change from Baseline to Month 6 in CD4+ Th2 cells (CCR4+)
6. Change from Baseline to Month 6 in CD4+ Th17 cells (CCR6+)
7. Change from Baseline to Month 6 in CD8+ naïve T cells (CCR7+CD45RA+)
8. Change from Baseline to Month 6 in CD8+ central memory T cells (CCR7+CD45RACD45RO+)
9. Change from Baseline to Month 6 in CD8+ effector memory T cells (CCR7-CD45RACD45RO+)
10. Change from Baseline to Month 6 in naïve B Lymphocytes (CD19+CD27-)
11. Change from Baseline to Month 6 in memory B Lymphocytes (CD19+CD27+)
12. Change from Baseline to Month 6 in regulatory B Lymphocytes (CD19+CD24+CD38+)
13. Change from Baseline to Month 6 in monocytes (CD14+)
14. Change from Baseline to Month 6 in neutrophils (CD16+)
15. Change from Baseline to Month 6 in NK cells (CD56+)
16. Change from Baseline to Month 6 in Total CD4+ Absolute Cell Counts
17. Change from Baseline to Month 6 in Total CD4+ Differential Cell Counts
18. Change from Baseline to Month 6 in Total CD8+ Absolute Cell Counts
19. Change from Baseline to Month 6 in Total CD8+ Differential Cell Counts
20. Change from Baseline to Month 6 in Total CD19+ Absolute Cell Counts
21. Change from Baseline to Month 6 in Total CD19+ Differential Cell Counts

Descriptive statistics (sample size, mean, standard deviation, standard error of mean, minimum, first quartile, median, third quartile, interquartile range, and maximum) will be provided. The 95% confidence interval for the mean will be calculated.

Analyses will be performed with respect to the actual value of primary variables by employing an analysis of covariance (ANCOVA) model with gender as a factor and duration of disease at Baseline (either time since first symptom or time since diagnosis) and corresponding baseline as covariates. The unadjusted as well as the adjusted least squares means will be provided together with a p-value.

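### Biomarker samples are assigned to Months 3, 6 and 12 by study day alone, so post-drug discontinuation samples and event-driven unscheduled samples can stand in for the scheduled on-fingolimod value

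*SAP*

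**What the plan says.** **Windows.** SAP 2.1.1 assigns laboratory data by study day: "Observations from Day 2 through Day 135 will be assigned to the 3-month visit", then "Days 136 through Day 270 will be assigned to the 6-month visit, and Days 271 and beyond will be assigned to the 12-month visit". For several samples in one window the rule is "If more than one observation occurs within a given window, the one closest to the target day will be used". No target day is given. SAP 2.7.1 builds the window into the primary endpoint: "Change from baseline to Month 6 = Observed Value at Month 6 (Days 136 to 270) – Baseline Value".

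**Population.** The biomarker analyses use the Safety Set, whose members need only have "received at least one dose of fingolimod during the study" (SAP 2.2). Neither document restricts biomarker samples to those taken on drug.

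**Extra samples.** Protocol Table 6-1 marks blood collection in the Month 12/SDC column and in the unscheduled-visit column. Protocol 5.6.2.1 times the SDC visit from the last fingolimod dose, with a 14-day target, and accepts later returns: "In case this Visit does not occur within 14 Days then the date when the patient returns must be documented". Protocol 5.6.2 adds: "An unscheduled visit (UNS) is a spontaneous visit and may take place at any time during the course of the clinical trial".

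**Limits elsewhere.** SAP 2.8.4 and 2.8.4.1 cut off treatment-emergent adverse events and on-treatment deaths at 14 days after the last dose. There is no counterpart for biomarkers. Protocol 9.4.4 lists sensitivity analyses as not applicable.

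**The concern.** The secondary objective concerns patients on fingolimod therapy, and the primary objective describes two cohorts that continue treatment for 12 months. The window rule, followed exactly, does not deliver that population of samples.

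- An SDC sample taken after the last dose can become the Month 3, 6 or 12 value for a patient who never reached that visit. Someone who leaves on Day 140 supplies a Month 6 value.
- An unscheduled sample, drawn because the investigator saw a need, can fill an empty window. It can also replace the scheduled sample if it lies nearer the target day.
- A sample from Day 2 of treatment can be reported as Month 3.

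The two cohorts are exposed differently. In Cohort 1 off-drug values dilute a large change. In Cohort 2 the baseline is already on drug and little further change is expected, so a few off-drug values can look like a real shift. Protocol 3.2 calls the repeated time points particularly relevant to that cohort.

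**Working it through.** **1. The plan's own figures.** A two-sided one-sample t-test on the change, with n = 200, effect size 0.30 and alpha = 0.05/15, has 89.6% power (stated: 89%). The 95% half-width is 1.96/√200 = 0.139 SD (stated: 0.14). Both reproduce.

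**2. Window widths.** Take Day 1 as the baseline visit in both cohorts, as in Table 6-1, and assume target days of 91 and 182.

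| Visit | Protocol window | SAP window | Ratio |
|---|---|---|---|
| Month 3 | 91 ± 7: Days 84–98, 15 days | Days 2–135, 134 days | 134/15 = 8.9 |
| Month 6 | 182 ± 14: Days 168–196, 29 days | Days 136–270, 135 days | 135/29 = 4.7 |
| Month 12 | ± 14 days | Day 271 onward | no upper limit |

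With a Day 182 target, an unscheduled sample on Day 185 would displace a scheduled one on Day 196, although the latter is within the protocol window.

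**3. Size of bias, total lymphocytes only.** Protocol 1.1 puts chronic on-drug counts at about 30% of baseline, a deficit of 70%. Let f be the share of window values that are off drug and r the share of the deficit recovered. Both are assumptions.

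- An off-drug value averages 0.30 + 0.70r of the pre-drug level, so the window mean rises by 0.70·f·r.
- Cohort 2, relative to its on-drug baseline: f·r·0.70/0.30.
- Cohort 1, relative to its pre-drug baseline: −70% × (1 − f·r).

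| f | r | Cohort 2 spurious rise | Cohort 1 change (true −70%) |
|---|---|---|---|
| 2% | 25% | 1.2% | −69.65% |
| 2% | 50% | 2.3% | −69.3% |
| 2% | 100% | 4.7% | −68.6% |
| 5% | 25% | 2.9% | −69.12% |
| 5% | 50% | 5.8% | −68.25% |
| 5% | 100% | 11.7% | −66.5% |
| 10% | 25% | 5.8% | −68.25% |
| 10% | 50% | 11.7% | −66.5% |
| 10% | 100% | 23.3% | −63.0% |

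**4. Against the planned precision.** In SD units the Cohort 2 bias is f × k, where k is the assumed shift of an off-drug sample in SDs. With f = 5%, k = 1 gives 0.05 SD, well inside 0.14, and k = 3 gives 0.15 SD, just beyond it. With f = 2%, even k = 3 gives only 0.06 SD.

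**5. Power in Cohort 1.** Scaling the design effect to 0.30 × (1 − f·r), with the SD unchanged, gives 0.2985 down to 0.27 over the grid, and power from 89.3% down to 80.0%.

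**6. Cost of excluding the samples.** For 2%, 5% and 10% excluded, n is 196, 190 and 180. Power is 88.8%, 87.5% and 85.1%, and the half-width is 0.141, 0.143 and 0.147 SD.

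**The case against.** A reader might infer that the biomarker results are contaminated. The documents do not show that, and several points count against it.

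- **SDC need not mean off drug.** The visit is triggered by leaving the study. The drug is commercial and not supplied by the sponsor, so a patient may leave and keep taking it.
- **Late SDC visits are the exception.** Table 6-1 gives SDC a window of under 14 days. Later returns are accepted, but they depart from that target. Each discontinuer normally gives one SDC sample, in one window, and it matters only if no sample lies nearer the target day.
- **Unscheduled samples are mainly a timing and selection issue.** Nothing suggests that they are usually off drug, and neither the direction nor the size of any selection is known.
- **The 30% figure covers total lymphocytes.** The Protocol describes effector memory T cells as largely spared (1.1), and reports that monocytes and NK cells expanded on treatment in the earlier studies (3.2). Recovery could lower those two. No depletion figure is given for neutrophils.
- **The setting is descriptive.** SAP 2.7.2 states that there is no confirmatory hypothesis. Medians and quartiles, which resist a few outlying values, accompany the means.
- **Exclusion has its own bias.** Dropping off-drug values conditions on a post-baseline event, with no imputation.

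All of this stands and limits the size of the problem. It does not remove it: the written rule admits these samples, the SAP nowhere says that values are meant to count regardless of discontinuation, and no planned analysis would reveal their influence. The table column shared by SDC and Month 12 may mean only that the same assessments are done, but then the analysis visit for SDC samples still has to be stated.

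**Conclusion.** The point holds as a defect of the rule, not as a demonstrated bias. Day-only windows with an undefined target day can count a post-drug, event-driven or very early sample as an on-fingolimod Month 3, 6 or 12 value. The SAP applies a last-dose limit to adverse events and deaths but not to its primary variables.

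The size is unknown. For total lymphocytes, under f = 2–10% and r = 25–100%, the Cohort 2 rise runs from 1.2% to 23.3% and the Cohort 1 change from −69.65% to −63.0%. At f = 2% the effect is small in both cohorts. It becomes comparable with the planned precision only towards the upper end of the assumed range, and chiefly in Cohort 2. For monocytes and NK cells the direction may reverse, and effector memory cells may be little affected. The open end of the Month 12 window probably matters least, since the last planned visit falls there. The change should be made before the analysis because it is cheap and the rule touches every primary variable.

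**What to change.** In SAP 2.1.1 and 2.7.1:

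1. Base the main biomarker analysis on samples taken on fingolimod. Use a flag derived from the last-dose date and a maximum gap that the sponsor fixes in advance and justifies. A 14-day gap would still admit SDC samples taken on time after the drug was stopped, so the choice needs a reason. Keep the all-samples analysis as a sensitivity analysis.
2. Define the target days, and let the scheduled visit take precedence over unscheduled samples in the same window.
3. Give Month 3 a later lower bound, for example the midpoint between Day 1 and the target day (Day 46 if the target is Day 91). Give Month 12 an upper bound. State which analysis visit, if any, an SDC sample belongs to, and reconcile this with Table 6-1.

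**Cost.** This takes SAP wording and one derived flag; SAP 2.1.1 and 2.6 already derive last-dose dates and days off treatment. Somewhat fewer samples are evaluable: at an assumed 5% excluded, power is about 87.5% and the half-width 0.143 SD. Excluding discontinuers brings some selection, which the comparison with the all-samples analysis would help to show.

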2.2 Analysis sets

Enrolled Set: All patients enrolled in one of the two cohorts will be included in the Enrolled Set.

Safety Set: The Safety Set will include all patients who enrolled in one of the two cohorts and received at least one dose of fingolimod during the study. Patients will be analyzed according to the cohort enrolled.

Full Analysis Set: For this study, the Full Analysis Set is the same as the safety set defined above.

2.3 Patient disposition, demographics and other baseline characteristics

2.3.1 Patient disposition

The number of patients enrolled, number of screen failure, patients treated, reasons for not receiving fingolimod treatment, patients who discontinued the fingolimod treatment and reasons for fingolimod treatment discontinuation, number and percentage of patients by end of study status will be summarized.

In addition, the number of patients in each analysis population and reasons for exclusion from a population will also be summarized.

A listing of patient disposition will be provided for all enrolled patients, with the extent of their participation in the study and the reason for discontinuation.

2.3.2 Protocol Deviations

Major protocol deviations will be summarized by cohort. All protocol deviations will be listed, with a flag indicating major or minor.

2.3.3 Demographics

Demographics (age, gender, race, and ethnicity) will be summarized by cohort for the Safety Set.

2.3.4 MS History/Baseline disease characteristics

Baseline disease characteristics will be summarized by cohort for the Safety Set.

- Time (in years) from MS diagnosis to first treatment date, calculated as: (Date of MS diagnosis – date of Day 1 + 1)/ 365.25.
- Time (in years) from first MS symptoms to first treatment date, calculated as: (Date of first MS diagnosis – date of Day 1 + 1)/ 365.25.
- Number of relapses in the last year/ Number of required steroids
- Number of relapses in the last 2 years/ Number of required steroids
- Time (in years) from most recent relapse to Day 1, calculated as: (Date of MS diagnosis – date of Day 1 + 1)/ 365.25.

Listings will be provided for demographic and baseline disease characteristics.

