6.4.5 Drug regimen

For patients in Cohort 2, date of first treatment, dose and frequency will be reported at Visit 1/Screening eCRF. At Visit 2/ Baseline date of treatment, dose and frequency will be reported for both Treatment Cohorts in the eCRF.

At the subsequent visits, patient compliance will be reported: if the patient is taking their medication regularly as prescribed, if the patient has missed any doses and how often the patients have missed their dose. All information will be recorded in the eCRF at the Visits as outlined in the [Table 6-1](#)

The investigator/qualified site staff should promote compliance by instructing patients to attend the study visits as scheduled, to take the fingolimod treatment exactly as prescribed, and reiterate that compliance is necessary for patient safety and the validity of the study.

Patients should be instructed to contact the investigator/qualified site staff if he/she is unable for any reason to attend a study visit as scheduled, or if he/she is unable for any reason to take their prescribed treatment.

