2.1 Data analysis general information

Interim analysis/final analysis will be performed [REDACTED]

SAS® Software version 9.4 or later will be used in this study as primary statistical analysis software.

Statistical methods used in reporting for both efficacy and safety are described below.

In general, categorical measurements will be summarized by frequency counts and percentages. Continuous variables will be summarized by numbers of patients, means, standard deviations, standard error of mean, first quartile, medians, third quartile, interquartile range, minimums, and maximums.

In summary statistics of means and medians, one more decimal place beyond the reported data will be displayed, and 2 more decimal places will be displayed for the standard deviation. The minimum and maximum will keep the same decimal places as the reported data.

Statistical tests will be performed at a 2-sided significance level of 0.05 unless otherwise stated. All p-values will be rounded up to 4 decimal places. For example, any p-value strictly greater than 0.0049 and less than or equal to 0.0050 will be displayed as 0.0050. This guarantees that on any printed statistical output, the unrounded p-value will always be less than or equal to the displayed p-value. A displayed p-value of 0.0001 will always be understood to mean ≤ 0.0001 . Likewise, any p-value displayed as 1.0000 will be understood to mean > 0.9999 and ≤ 1 .

All collected data from the eCRFs (including electronic data) and derived analytical data will be included in the listing.

All summaries will be presented by Cohort.

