2.4 Past or present MS symptoms with Location

Number of each MS symptom/location/persistency/severity by prior and post fingolimod treatment will be provided for the Safety Set.

All past and present MS symptoms will be listed for the Safety Set.

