2.6 Fingolimod treatment / compliance / Dose interruption

The duration of fingolimod treatment exposure (days) for patients who took at least one dose of fingolimod treatment will be summarized with descriptive statistics. Duration will be calculated as:

Duration of exposure (days) = (Date of last administration of fingolimod treatment – Date of first administration of fingolimod treatment) +1 .

The actual number of days of fingolimod treatment exposure will be calculated as:

Actual days of fingolimod treatment exposure = (Date of last administration of fingolimod treatment – Date of first administration of fingolimod treatment) +1 – days not on treatment.

Compliance(%) will be calculated as:

Compliance (%) = actual days of fingolimod treatment exposure / duration of exposure *100

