5.1 Imputation rules

In general, other than for partial dates, missing data will not be imputed and will be treated as missing.

Partial date will be imputed as below:

- If year is missing (or completely missing), do not impute;
- 15th of the month will be used to impute the initial diagnosis date if only the day is missing;
- July of the year will be used to impute as the initial diagnosis date if both the day and the month are missing;

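### SAP 2.3.4: all three disease-history durations are subtracted in the wrong order, and the first-symptom and last-relapse rows use a diagnosis date

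*SAP*

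**What the plan says.** SAP 2.3.4 lists three durations in years among the baseline disease characteristics, summarised by cohort:

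- Row 1, the time "from MS diagnosis to first treatment date, calculated as: (Date of MS diagnosis – date of Day 1 + 1)/ 365.25".
- Row 2, the time "from first MS symptoms to first treatment date, calculated as: (Date of first MS diagnosis – date of Day 1 + 1)/ 365.25".
- Row 3, the time "from most recent relapse to Day 1, calculated as: (Date of MS diagnosis – date of Day 1 + 1)/ 365.25".

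For treatment exposure, SAP 2.6 uses the opposite order: "Duration of exposure (days) = (Date of last administration of fingolimod treatment – Date of first administration of fingolimod treatment) +1".

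SAP 5.1 refers to one diagnosis date only: "15th of the month will be used to impute the initial diagnosis date if only the day is missing". SAP 2.7.1 adjusts the primary ANCOVA for disease duration at Baseline, measured from either first symptom or diagnosis, and does not point to 2.3.4 for the derivation.

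On the reference date, SAP 2.1.1 defines Day 1 as the date of the first non-zero fingolimod dose, while protocol 3.1 treats Baseline, at the end of screening, as Day 1. Protocol 6.4.5 adds: "For patients in Cohort 2, date of first treatment, dose and frequency will be reported at Visit 1/Screening eCRF".

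**The concern.** There are two separate errors. First, each row is a time from an earlier event to a later one, yet each formula takes the later date away from the earlier. Second, rows 2 and 3 do not contain the date their labels name: no symptom date and no relapse date enters any of the formulas. No other section of either document gives a correct derivation.

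The second error is the one that could survive into the report. Negative years would be noticed and the order reversed. The output would then look plausible while two of the three rows still measured the wrong interval. The study is nonrandomized with two cohorts, and the baseline table is where a reader judges how their disease histories differ.

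There is a related labelling problem. Rows 1 and 2 run to first treatment but use Day 1. A Cohort 2 patient first took fingolimod at least two years before study Baseline, so the two readings of Day 1 give different answers.

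**Working it through.** The documents give no numerical result for these rows, so there is no figure to reproduce. The check applies the formulas to one patient with assumed dates: first symptoms 1 Jan 2006, diagnosis 1 Jan 2008, last relapse 1 Jul 2017, Day 1 on 1 Jan 2018.

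**Days from event to Day 1:** symptoms 4383, diagnosis 3653, relapse 184.

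**As written**, taking the two diagnosis wordings as one date: (-3653 + 1)/365.25 = -3652/365.25 = -10.00 years in every row.

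**Order corrected only:** (3653 + 1)/365.25 = 3654/365.25 = +10.00 years in every row.

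**Order and dates corrected:**

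| Row | Calculation | Correct (years) | As written | Order corrected only |
|---|---|---|---|---|
| Diagnosis | 3654/365.25 | 10.00 | -10.00 | 10.00 |
| First symptoms | 4384/365.25 | 12.00 | -10.00 | 10.00 (2.00 too short) |
| Last relapse | 185/365.25 | 0.51 | -10.00 | 10.00 (9.50 too long) |

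**When the sign is not negative.** Diagnosis on Day 1 gives 1/365.25 = 0.003 years, and diagnosis the day before gives 0. Anything earlier is negative.

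**Cohort 2 reference date.** Take the same patient with a first-ever dose on 1 Jan 2016, 731 days before Baseline. With corrected formulas measured to that dose:

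- diagnosis: (3653 - 731 + 1)/365.25 = 2923/365.25 = 8.00 years
- symptoms: (4383 - 731 + 1)/365.25 = 3653/365.25 = 10.00 years
- relapse: (184 - 731 + 1)/365.25 = -546/365.25 = -1.49 years

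Measured to Baseline they are 10.00, 12.00 and 0.51.

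**Effect on the ANCOVA, if its covariate is taken from 2.3.4.** For the same event date, the value as written equals minus the correct value plus 2/365.25. This is a linear recoding: the duration coefficient changes sign, and the adjusted means at mean covariates and all p-values stay the same. Using the diagnosis date for the symptom option is a real substitution, but a small one. An illustrative simulation used 200 patients and 2,000 runs per setting. It assumed 70% of one gender with a 0.2 SD effect, a baseline coefficient of 0.5, a mean symptom-to-diagnosis lag of 2 or 5 years, and a duration effect of 0.1 or 0.3 SD per SD. The mean absolute shift in the adjusted mean was 0.001 to 0.005 SD, and the largest 95th percentile was 0.013 SD. The planned precision in SAP section 3 is 0.14 SD.

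**The case against.** The strongest reply is that this is a copying slip in a descriptive table of a mainly descriptive study. The row labels make the intended quantities plain, and a programmer would follow them. The source data are not lost: SAP 2.1 says "All collected data from the eCRFs (including electronic data) and derived analytical data will be included in the listing", and SAP 2.4 adds "All past and present MS symptoms will be listed for the Safety Set". SAP 2.7.1 names the covariate itself and does not cite 2.3.4, so the link to the ANCOVA is conditional. The claim that all three rows are identical also depends on reading the two diagnosis wordings as one date; without that, only rows 1 and 3 are certainly the same.

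On Cohort 2, SAP 2.1.1 equates Day 1 with first administration, so within the SAP the labels and formulas of rows 1 and 2 agree. The visit windows there (Days 2 to 135, 136 to 270, 271 onward) make sense only if Day 1 is study Baseline: counted from a first-ever dose at least two years earlier, every on-study visit would fall in the last window and no Month 6 value would exist.

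Much of this stands, and it limits the harm. It does not remove the error. The formulas are the stated derivations, and even if there are two diagnosis dates, neither is a symptom or relapse date. The windows do point to Baseline, but the first-dose wording of SAP 2.1.1 still conflicts with protocol 3.1 for Cohort 2, and one clarifying line is justified.

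**Conclusion.** The concern holds. All three formulas in SAP 2.3.4 reverse the subtraction, and two use the wrong event date. Followed literally, the rows show negative years for practically every patient. With only the order repaired, the symptom and relapse rows remain wrong, by 2.00 and 9.50 years in the worked example. Those sizes depend on the assumed dates; the pattern does not. The identity of all three rows, and of the two ANCOVA duration options, rests on there being one diagnosis date, which is how SAP 5.1 reads; for the ANCOVA it also requires that the covariate be taken from 2.3.4.

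The consequence is limited to three derived baseline rows. The reversed sign leaves the adjusted means and their p-values unchanged, and the wrong date is expected to move them negligibly. The formulas should be corrected before programming; the point does not threaten the primary results.

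**What to change.** Replace the three formulas in SAP 2.3.4 with:

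- diagnosis: (date of Day 1 - date of MS diagnosis + 1)/365.25
- first symptoms: (date of Day 1 - date of first MS symptom + 1)/365.25
- most recent relapse: (date of Day 1 - date of most recent relapse + 1)/365.25

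Add one line stating whether, for Cohort 2, these rows run to study Baseline or to the first-ever fingolimod dose, and label them to match.

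The cost is three formulas and one sentence, with no change to design or sample size. One check is needed. The SAP rows imply that first-symptom and last-relapse dates are collected, but protocol 6.4.4 mentions only relevant MS history in general terms, so confirm against the eCRF that both dates are recorded.
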